#### 2.2 Secondary Objectives

- For Cohorts 1-3 (Cohorts 1-2 active IP and Cohort 3 is placebo)
  - Demonstrate target protective concentration (NAC) value  $> 0.02$  U/mL (BoNT/A) or  $> 0.03$  U/mL (BoNT/B) at Day 120
  - To evaluate pharmacodynamic (PD) and anti-drug antibody (ADA) at pre-dose through the end of study
- Cohort 4 (only active IP)
  - Demonstrate target protective concentration (NAC) value of BoNT/A and BoNT/B at 2 hours post-dose
  - To assess pharmacokinetics (PK) at pre-dose through end of study
  - To evaluate pharmacodynamics (PD) and anti-drug antibody (ADA) at pre-dose through the end of study

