Vital sign assessments will be performed at all in-clinic study visits, including systolic and diastolic blood pressure (BP), heart rate (HR), and oral temperature. During screening and follow-up, a measurement that is a Grade 1 (as referenced in Protocol G03-52-01-002, v4.0, 14Apr2024, Appendix B) may be repeated once if the principal investigator believes a transient condition led to the aberrant value. Vital signs obtained at screening will serve as baseline values for the subject. Grade 1 values are allowable unless deemed clinically significant by the study Investigator.

- **Electrocardiogram (ECG)**

A 12-lead ECG will be performed at screening and reviewed by the study PI or a co-Investigator to assess the cardiac status of a subject for eligibility for enrollment.

- **Laboratory Evaluations**

Laboratory assessment schedule will follow the Schedule of Assessments in Appendix A. Detailed laboratory tests can be found in Section 8.5.2 of Protocol G03-52-01-002, v4.0, 14Apr2024.

- **Pharmacodynamic (PD) and Pharmacokinetic (PK) Assays**

Blood samples for PD assessment will be collected at pre-dose, 24 hours post-dose, and on Days 8, 15, 45 (prior to dosing) 49, 90, and 120 for all subjects in Cohorts 1-3. The first 25 subjects randomized for each DP lot of 50 mg and 100 mg doses and placebo will be tested at all 8 timepoints. The remaining samples from the subjects who received either dose or lot of G03-52-01 (including placebo) will only be tested using MNA at pre-dose and Days 45, 90, and 120.

Blood samples for PD assessment will be collected at pre-dose, 2 hours, 4 hours, 8 hours, 24 hours, and on Days 30, 45, and 90 for all subjects in Cohort 4. Cohort 4 samples for the first 30 subjects, who receive active drug product and complete sample collection at 24 hours, will be tested at pre-dose, 2 hours, 4 hours, 8 hours, 24 hours, and on Days 30, 45, and 90. PD samples will be analyzed for neutralizing antibody concentration (NAC) using the validated Battelle MNA.

Blood samples for PK assessment will be collected at pre-dose, 24 hours and 72 hours post-dose, and on Days 8, 15, 45 (prior to dosing), 49, 90, and 120 for all subjects in Cohorts 1-3. The first 25 subjects randomized for each DP lot of 50 mg and 100 mg doses and placebo will be tested at all timepoints.

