## Statistical Analysis Plan (SAP)

### 5 Study Endpoints

Table 2 summarizes the study endpoints in relation to their corresponding study objectives, as well as a brief overview of the statistical methods (described in greater detail in Section 8) used to analyze each endpoint.

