## Statistical Analysis Plan (SAP)

		confidence interval (CI) for GM, the geometric coefficient of variation (GCV, presented in percentage, GCV%), and the 95% CI of GCV% calculated for each time point for each cohort and DP lot
Secondary Objective #3: For Cohort 4 (only active IP): Demonstrate target protective concentration (NAC) value of BoNT/A and BoNT/B at 2 hours post-dose	Secondary Endpoint #3: To evaluate the proportion of subjects with target protective concentration (NAC) value > 0.02 U/mL (botulinum neurotoxin [BoNT]/A) or > 0.03 U/mL (BoNT/B) at 2 hours post dose	Protective NAC rate at 2 Hours post dose, where protective NAC rate is defined as the proportion of subjects with NAC value > 0.02 U/mL against BoNT/A or NAC value > 0.03 U/mL against BoNT/B
Secondary Objective #4: For Cohort 4 (only active IP): To assess pharmacokinetics (PK) at pre-dose through end of study	Secondary Endpoint #4: PK analysis at the determined timepoints	Summary statistics [number of subjects (n), mean, SD, median, first quartile, third quartile, minimum, maximum], CV%, GM, the 95% CI for GM, GCV%, and the 95% CI of GCV% calculated for each time point for the Cohort 4 active G03-52-01 treatment group
Secondary Objective #5: For Cohort 4 (only active IP): To evaluate pharmacodynamics (PD) and anti-drug antibody (ADA) at pre-dose through the end of study	Secondary Endpoint #5: Descriptive statistics of determined PD and ADA timepoints	Summary statistics [number of subjects (n), mean, SD, median, first quartile, third quartile, minimum, maximum], CV%, GM, the 95% CI for GM, GCV%, and the 95% CI of GCV% calculated for each time point for the Cohort 4 active G03-52-01 treatment group
Exploratory Objective	Exploratory Endpoint	Statistical Methodology
Exploratory Objective: For Cohorts 1-3 (Cohorts 1-2 active IP and Cohort 3 is placebo): To evaluate PK parameters to ensure ADA evaluation adequate of the two lots	Exploratory Endpoint: Descriptive statistics of selected PK parameters at all time points tested of the two lots	Summary statistics [number of subjects (n), mean, SD, median, first quartile, third quartile, minimum, maximum], CV%, GM, the 95% CI for GM, GCV%, and the 95% CI of GCV% calculated for each time point for each cohort and DP lot

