### 9.10.3 Primary Endpoint 2 – Target Protective NAC (Day 45 and Day 90), Cohorts 1-2

To evaluate primary objective #2, to demonstrate target protective concentration (NAC) value of BoNT/A and BoNT/B through Day 45 and Day 90 for Cohorts 1-2, primary endpoint #2 will be used:

For Cohorts 1-2, to evaluate target protective concentration (NAC) value  $> 0.02$  U/mL (BoNT/A) or  $> 0.03$  U/mL (BoNT/B) at Day 45 and Day 90

PD samples will be collected and analyzed by the Battelle MNA against serotypes BoNT/A and BoNT/B at Baseline/Dosing [Visit 2 (Day 1)] pre-dose, Visit 3 (24 Hours), Visit 5 (Day 8), Visit 6 (Day 15), Visit 7 (Day 45) pre-dose, Visit 8 (Day 49), Visit 10 (Day 90), and Visit 11 (Day 120).

At Visit 7 (Day 45) and Visit 10 (Day 90), the frequency and percentage of subjects with a NAC  $> 0.02$  U/mL against BoNT/A, a NAC  $> 0.03$  against BoNT/B, and those with either a NAC  $> 0.02$  U/mL against BoNT/A or a NAC  $> 0.03$  U/mL against BoNT/B will be presented. Percentages will be based on the total number of subjects at the respective time point with evaluable concentrations. Summaries will be presented for each lot separately within each of the two active drug cohorts.

The PD population will be used for the analysis of this primary endpoint.

### 9.10.4 Primary Endpoint 3 – Target Protective NAC (4 Hours and 8 Hours), Cohort 4

To evaluate primary objective #3, to demonstrate target protective concentration (NAC) value of BoNT/A and BoNT/B at 4 and 8 Hours post-dose for Cohort 4 (active only), primary endpoint #3 will be used.

At 4 Hours post-dose and 8 Hours post-dose, the frequency and percentage of subjects with a NAC  $> 0.02$  U/mL against BoNT/A, a NAC  $> 0.03$  against BoNT/B, and those with either a NAC  $> 0.02$  U/mL against BoNT/A or a NAC  $> 0.03$  U/mL against BoNT/B will be presented. Percentages will be based on the total number of subjects at the respective time point with evaluable concentrations. Summaries will be presented for each lot separately within each of the two active drug cohorts.

The PD population will be used for the analysis of this primary endpoint.

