## Statistical Analysis Plan (SAP)

---

```
var x;  
ods select ConfLimits;  
run;
```

, where `indata` is the data set with PD parameters and `x` is a parameter.

Additionally, PD parameters and NAC values will be listed separately at the subject level.

The PD population will be used for all pharmacodynamic tables, listings, and figures.

Immunogenicity (ADA) samples will be tested at Baseline/Dosing [Visit 2 (Day 1)] pre-dose, Visit 3 (24 Hours) and Visit 4 (72 Hours) post-dose, and at Visit 5 (Day 8), Visit 6 (Day 15), Visit 7 (Day 45) pre-dose, Visit 8 (Day 49), Visit 10 (Day 90), Visit 11 (Day 120), Visit 12 (Day 150), Visit 13 (Day 180), and Visit 14 (Day 240).

The frequency and percentage of subjects with a positive immunogenicity response will be summarized by time point across the active treatment arms. Additionally, anti-drug antibody titers will be summarized using continuous descriptive statistics [number of subjects (n), mean, SD, median, Q1, Q3, minimum, maximum, CV%, GM, GCV%, and the 95% CI of the GCV] by time point. Both the categorical and continuous ADA table summaries will include a subgroup analysis for only those subjects that have a negative immunogenicity response at baseline. Anti-drug antibody status and titer values will be listed by subject and time point.

The ITT population will be used for all immunogenicity summaries.

### 9.10.7 Secondary Endpoint 3 – Target Protective NAC (2 Hours), Cohort 4

To evaluate secondary objective #3, demonstrate target protective concentration (NAC) value of BoNT/A and BoNT/B at 4 and 8 hours post-dose (Cohort 4), secondary endpoint #3 will be used.

To evaluate the proportion of subjects with target protective concentration (NAC) value > 0.02 U/mL (botulinum neurotoxin [BoNT]/A) or > 0.03 U/mL (BoNT/B) at 2 hours post dose

At the 4 Hour and 8 Hour post-dose time points, the frequency and percentage of subjects with a NAC > 0.02 U/mL against BoNT/A, a NAC > 0.03 against BoNT/B, and those with either a NAC > 0.02 U/mL against BoNT/A or a NAC > 0.03 U/mL against BoNT/B will be presented. Percentages will be based on the total number of subjects at the respective time point with evaluable concentrations.

The PD population will be used for the analysis of this secondary endpoint.

### 9.10.8 Secondary Endpoint 4 – PK Evaluation, Cohort 4

To evaluate secondary objective #4, to assess pharmacokinetics (PK) at pre-dose through end of study (Cohort 4), secondary endpoint #4 will be used.

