## Statistical Analysis Plan (SAP)

---

Additionally, NAC values will be summarized descriptively for each serotype separately at Baseline/Dosing [Visit 2 (Day 1)] pre-dose, Visit 3 (24 Hours), Visit 7 (Day 30), Visit 8 (Day 45), and Visit 9 (Day 90). Concentration-time profiles will be displayed graphically on linear and semi-log scales by serotype and active treatment group. One set of plots will include error bars (presented as SD) and one set will not include error bars.

The summary statistics used for all PD parameters and concentrations will include number of subjects (n), mean, SD, median, Q1, Q3, minimum, maximum, CV%, GM, the 95% CI of the GM, GCV%, and the 95% CI of GCV%.

The GM, 95% CI of GM, GCV%, and 95% CI of GCV% will be calculated using the following SAS® procedure:

```
proc ttest data=indata dist=lognormal;
  var x;
  ods select ConfLimits;
run;
```

, where `indata` is the data set with PD parameters and `x` is a parameter.

Additionally, PD parameters and NAC values will be listed separately at the subject level.

The PD population will be used for all pharmacodynamic tables, listings, and figures.

Immunogenicity (ADA) samples will be collected at Baseline/Dosing [Visit 2 (Day 1)] pre-dose, Visit 9 (Day 90), and Visit 10 (Day 120).

The frequency and percentage of subjects with a positive immunogenicity response will be summarized by mAb and time point across the active treatment arms. Results will be categorized as Detected, Not Detected, and NRR (No Recorded Result). Additionally, anti-drug antibody titers for the overall drug product will be summarized using continuous descriptive statistics [number of subjects (n), mean, SD, median, Q1, Q3, minimum, maximum, CV%, GM, 95% CI of the GM, GCV%, and the 95% CI of the GCV] by the aforementioned time points. Both the categorical and continuous ADA table summaries will include a subgroup analysis for only those subjects that have a negative immunogenicity response at baseline. Anti-drug antibody status and titer values will be listed by subject and time point.

The ITT population will be used for all immunogenicity summaries.

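### Three SAP analysis sections name the wrong time points: read literally, the 2-hour Cohort 4 NAC rate is never tabulated and the Day 60 ADA summary could be lost

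*SAP*

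**What the plan says.** **Cohort 4, 2-hour NAC.** The Cohort 4 secondary objective in SAP 2.2 is "Demonstrate target protective concentration (NAC) value of BoNT/A and BoNT/B at 2 hours post-dose". The Table 2 method for Secondary Endpoint 3 is "Protective NAC rate at 2 Hours post dose, where protective NAC rate is defined as the proportion of subjects" above the serotype thresholds. The heading of 9.10.7 and the endpoint sentence beneath it also say 2 hours. The sentence in 9.10.7 that restates the objective says 4 and 8 hours, and the sentence that specifies the table begins "At the 4 Hour and 8 Hour post-dose time points, the frequency and percentage of subjects". Section 9.10.4, for Primary Endpoint 3, already says "At 4 Hours post-dose and 8 Hours post-dose, the frequency and percentage of subjects with a NAC" above the threshold will be presented.

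**Cohort 4, descriptive NAC.** SAP 3.4 states that samples from the first 30 qualifying active subjects "will be tested at pre-dose, 2 hours, 4 hours, 8 hours, 24 hours, and on Days 30, 45, and 90". Section 9.10.9 plans descriptive NAC summaries at "Baseline/Dosing [Visit 2 (Day 1)] pre-dose, Visit 3 (24 Hours), Visit 7 (Day 30), Visit 8 (Day 45), and Visit 9 (Day 90").

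**Cohorts 1-2, ADA.** SAP 3.4 and Appendix A footnote 17 schedule ADA at pre-dose and Days 15, 45 (pre-dose), 60, 90, 120, 150, 180 and 240. Section 9.10.6 gives a different list, which starts with pre-dose, 24 hours, 72 hours, Day 8 and Day 15, continues with "Visit 7 (Day 45) pre-dose, Visit 8 (Day 49), Visit 10 (Day 90), Visit 11 (Day 120), Visit 12 (Day 150"), and ends with Days 180 and 240.

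**Which text governs.** SAP Section 5 describes Table 2 as listing the endpoints "as well as a brief overview of the statistical methods (described in greater detail in Section 8) used to analyze each endpoint". Section 8 covers derived variables, missing data and dates; the endpoint methods are in 9.10.

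**The concern.** The detailed methods text should settle what is programmed, and here it disagrees with the overview on a named secondary endpoint. Followed as written, 9.10.7 repeats a primary analysis and gives no 2-hour rate. The 9.10.9 list would not supply a 2-hour NAC summary either.

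The ADA error matters because Day 60 is the only ADA sample between the Day 45 pre-dose sample and Day 90. It is therefore the earliest look at immunogenicity after the repeat dose.

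There is also a reporting consequence. SAP Section 1 requires departures from the SAP to be described and justified in the CSR. Producing the intended 2-hour table departs from the tabulation sentence in 9.10.7, while following that sentence leaves out the endpoint. Section 10 declares no changes from the protocol, so nothing suggests that the differences are deliberate.

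**Working it through.** The check compares sets of time points within the SAP. The SAP cites protocol version 5.0 (06-JAN-2025) and the supplied protocol is dated 12 Apr 2024, so the comparison rests on SAP text only.

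**1. Secondary Endpoint 3 (Cohort 4)**

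- Statements giving 2 hours: SAP 2.2; the objective, endpoint and method cells of Table 2; the 9.10.7 heading; the 9.10.7 endpoint sentence. Total 6.
- Statements giving 4 and 8 hours: the 9.10.7 objective sentence and the 9.10.7 tabulation sentence. Total 2.
- Planned protective-rate times for Cohort 4: {2 h, 4 h, 8 h}. Times tabulated by 9.10.4 and 9.10.7 together: {4 h, 8 h}. Missing: {2 h}.

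**2. Descriptive NAC (Cohort 4)**

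- Tested (SAP 3.4): pre-dose, 2 h, 4 h, 8 h, 24 h, Days 30, 45, 90 = 8 times.
- Listed (9.10.9): pre-dose, 24 h, Days 30, 45, 90 = 5 times.
- Missing: 8 − 5 = 3, namely 2, 4 and 8 h.

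Steps 1 and 2 together show that no analysis sentence in 9.10 tabulates 2-hour NAC, either as a rate or as a descriptive summary. Only Table 2 does.

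**3. ADA visits (Cohorts 1-2)**

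| | Time points | Count |
|---|---|---|
| Scheduled (3.4; Appendix A footnote 17) | pre-dose, D15, D45, D60, D90, D120, D150, D180, D240 | 9 |
| Listed in 9.10.6 | pre-dose, 24 h, 72 h, D8, D15, D45, D49, D90, D120, D150, D180, D240 | 12 |
| Scheduled but not listed | D60 | 1 |
| Listed but not scheduled | 24 h, 72 h, D8, D49 | 4 |

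Six of the nine scheduled visits follow Dose 2 (Days 60, 90, 120, 150, 180, 240), and the omitted visit is the first of them. The first nine entries of the 9.10.6 list are exactly the nine PK times for Cohorts 1-3 in SAP 3.4. A copied PK schedule is the likely cause, though that is an inference.

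**4. Timing of the first ADA summary after Dose 2**

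Days 45, 60 and 90 each carry a ±3-day window, so Dose 2 falls on Days 42 to 48.

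- With Day 60: 60 − 45 = 15 days; range 57 − 48 = 9 to 63 − 42 = 21.
- Without Day 60: 90 − 45 = 45 days; range 87 − 48 = 39 to 93 − 42 = 51.

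**5. Lists that agree**

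The NAC list in 9.10.6 matches the schedule (8 of 8), as does the Cohort 4 ADA list in 9.10.9 (3 of 3). The faults are confined to the ADA list in 9.10.6, the NAC list in 9.10.9 and the two sentences in 9.10.7.

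**The case against.** The strongest reply is that these are drafting slips with one evident intended reading.

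- **2-hour rate.** The heading and endpoint sentence of 9.10.7 say 2 hours, and the faulty sentence refers to an objective that Table 2 defines at 2 hours. A programmer would probably notice that the literal text duplicates 9.10.4.
- **Day 60 ADA.** The 9.10.6 list describes when samples are tested. The summary rule that follows says only by time point, and Table 2 calls for ADA at every time point tested. A by-time-point summary of the data would include Day 60, and the four unscheduled visits would simply be empty.
- **Descriptive NAC.** The 9.10.9 list is incomplete rather than wrong. Table 2 asks for statistics at each time point in the Cohort 4 active group, and 9.10.4 already gives the 4- and 8-hour rates.
- **Outputs.** The table shells are in a separate document not seen here, subject listings would hold every value, and there is no formal hypothesis testing.

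These points stand as limits on the consequences: the data are not lost, and it cannot be shown that a table will be missing. They also separate the three faults. Only 9.10.7 contradicts its own heading and objective; 9.10.6 conflicts with the sampling schedule, and 9.10.9 errs by omission. They do not remove the contradictions. Someone could reasonably follow the detailed section over a table that the SAP itself calls a brief overview. The Section 5 pointer to Section 8 is minor alone, but it leaves the order of precedence less clear.

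**Conclusion.** The concern holds and should be fixed. All three mismatches are in the current final SAP (v2.0). The most consequential is 9.10.7: as written, a named secondary endpoint has no tabulation sentence anywhere in 9.10. The 9.10.9 omission covers 3 of 8 tested times, in the 30 active subjects whose samples are assayed. The ADA list omits 1 of 9 scheduled visits and adds 4 that have no sample. The shift from 15 to 45 days after Dose 2 applies only if the 9.10.6 list is taken as exhaustive.

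What is at risk is the tabulated summaries of secondary, descriptive endpoints. No primary conclusion is affected. The finding assumes a literal reading of 9.10 and has not been checked against the table shells.

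**What to change.** - **9.10.7:** change the objective sentence and the tabulation sentence to 2 hours post-dose.
- **9.10.9:** add 2, 4 and 8 hours to the descriptive NAC summary times.
- **9.10.6:** replace the ADA visit list with pre-dose and Days 15, 45 (pre-dose), 60, 90, 120, 150, 180 and 240, in line with SAP 3.4 and Appendix A footnote 17.
- **Section 5:** redirect the cross-reference from Section 8 to Section 9.10.
- **Table shells:** check them against these four changes.

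The cost is SAP wording and a shell check. The samples are already scheduled, so no new visit or assay is needed.

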## Statistical Analysis Plan (SAP)

---

Additionally, NAC values will be summarized descriptively for each serotype separately at Baseline/Dosing [Visit 2 (Day 1)] pre-dose, Visit 3 (24 Hours), Visit 7 (Day 30), Visit 8 (Day 45), and Visit 9 (Day 90). Concentration-time profiles will be displayed graphically on linear and semi-log scales by serotype and active treatment group. One set of plots will include error bars (presented as SD) and one set will not include error bars.

The summary statistics used for all PD parameters and concentrations will include number of subjects (n), mean, SD, median, Q1, Q3, minimum, maximum, CV%, GM, the 95% CI of the GM, GCV%, and the 95% CI of GCV%.

The GM, 95% CI of GM, GCV%, and 95% CI of GCV% will be calculated using the following SAS® procedure:

```
proc ttest data=indata dist=lognormal;
  var x;
  ods select ConfLimits;
run;
```

, where `indata` is the data set with PD parameters and `x` is a parameter.

Additionally, PD parameters and NAC values will be listed separately at the subject level.

The PD population will be used for all pharmacodynamic tables, listings, and figures.

Immunogenicity (ADA) samples will be collected at Baseline/Dosing [Visit 2 (Day 1)] pre-dose, Visit 9 (Day 90), and Visit 10 (Day 120).

The frequency and percentage of subjects with a positive immunogenicity response will be summarized by mAb and time point across the active treatment arms. Results will be categorized as Detected, Not Detected, and NRR (No Recorded Result). Additionally, anti-drug antibody titers for the overall drug product will be summarized using continuous descriptive statistics [number of subjects (n), mean, SD, median, Q1, Q3, minimum, maximum, CV%, GM, 95% CI of the GM, GCV%, and the 95% CI of the GCV] by the aforementioned time points. Both the categorical and continuous ADA table summaries will include a subgroup analysis for only those subjects that have a negative immunogenicity response at baseline. Anti-drug antibody status and titer values will be listed by subject and time point.

The ITT population will be used for all immunogenicity summaries.

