PD samples will be tested by the Battelle Mouse Neutralization Assay (MNA) for serotypes A and B at pre-dose, 24 hours post dose, and on Days 8, 15, 45 (before repeat-dose), 49, 90, and 120. The first 25 subjects randomized for each drug product (DP) lot of 50 mg and 100 mg doses and placebo will be tested at all 8 timepoints. The remaining samples from the subjects who received either dose or lot of G03-52-01 (including placebo) will only be tested using MNA at pre-dose and Days 45, 90, and 120.

PK samples will be tested by electrochemiluminescence assay (ECLA) or enzyme-linked immunosorbent assay (ELISA) at pre-dose, 24 hours and 72 hours post dose, and on Days 8, 15, 45 (before repeat-dose), 49, 90, and 120. A total of 25 subjects for each DP lot of 50 mg and 100 mg doses and placebo will be tested at all timepoints.

For Cohort 4, PK and PD samples will be tested for the first 30 subjects who receive active drug and complete sample collection at 24 hours. PD samples will be tested by the Battelle Mouse Neutralization Assay (MNA) for serotypes A and B at pre-dose, 2 hours, 4 hours, 8 hours, 24 hours and on Days 30, and 45 and 90. PK samples will be tested by electrochemiluminescence assay (ECLA) or enzyme-linked immunosorbent assay (ELISA) at pre-dose, 2 hours, 4 hours, 8 hours, 24 hours, 72 hours post dose, and on Days 8, 15, 30, 45, 90, and 120.

ADA samples will be tested at pre-dose and Days 15, 45 (before repeat-dose or placebo), 60, 90, 120, 150, 180, and 240 for study subjects in Cohorts 1-3; and at pre-dose and post-dose on Days 90 and 120 for Cohort 4.

An interim Clinical Study Report (CSR) is planned for the first 125 subjects in Cohorts 1-3 through Day 120.

Study Population:

625 healthy male and female subjects between the ages of 18 and 65 years of age

Inclusion Criteria:

1. Informed consent understood and signed prior to screening procedures.

2. Assessed by the Investigator to be a healthy male or healthy, non-pregnant, non-lactating female between the ages of 18 and 65 inclusive on the day of dosing.
3. Able and willing to comply and be available for all protocol procedures and follow-up for the duration of the study.
4. Body Mass Index (BMI) of ≥ 18.5 and ≤ 35 kg/m².
5. Females of child-bearing potential must have a negative serum pregnancy test at screening and negative urine pregnancy test on Day 1 prior to dosing.

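### Cohort 4: the protective-NAC rate stops at 8 hours although NAC is assayed to Day 90, and the planned continuous summaries do not reliably stand in for it

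*SAP*

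**What the plan says.** **Assay times.** SAP 3.4 states that the Cohort 4 samples "will be tested at pre-dose, 2 hours, 4 hours, 8 hours, 24 hours, and on Days 30, 45, and 90". That is seven post-dose times. The Protocol synopsis limits testing (the last figure is in hours): "For Cohort 4, PK and PD samples will be tested for the first 30 subjects who receive active drug and complete sample collection at 24".

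**Times with a rate.** SAP 9.10.4 (Primary Endpoint 3) reads: "At 4 Hours post-dose and 8 Hours post-dose, the frequency and percentage of subjects with a NAC" above target, for each serotype and for either. SAP Table 2 defines Secondary Endpoint 3 as "Protective NAC rate at 2 Hours post dose, where protective NAC rate is defined as the proportion of subjects with NAC value" above the same thresholds. The method text for that endpoint in 9.10.7 instead reads "At the 4 Hour and 8 Hour post-dose time points, the frequency and percentage of subjects with a NAC", which repeats the primary times.

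**After 8 hours.** SAP 9.10.9 states: "Additionally, NAC values will be summarized descriptively for each serotype separately at Baseline/Dosing". The planned statistics are continuous (n, mean, SD, quartiles, minimum, maximum, CV%, geometric mean and GCV% with intervals), plus plots and subject listings. The post-dose visits it names are "Visit 3 (24 Hours), Visit 7 (Day 30), Visit 8 (Day 45), and Visit 9 (Day 90". It plans no proportion above target. It also leaves 2, 4 and 8 hours out of this list.

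**Objective.** SAP 2.2 sets for Cohort 4: "To evaluate pharmacodynamics (PD) and anti-drug antibody (ADA) at pre-dose through the end of study".

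**Below-quantitation values.** SAP 8.3 covers PD and PK analyses together. A BLQ value before the first measurable concentration becomes zero. A BLQ value after it becomes missing.

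**Cohort 2.** Subjects receive 100 mg on Day 1 and again on Day 45. The Day 45 sample is taken before the second dose, and the rate at Days 45 and 90 is Primary Endpoint 2, reported by lot (SAP 9.10.3).

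**The concern.** The trial expresses protection as a proportion of subjects above a serotype-specific target. Protocol 3.1.3 describes a product for pre-exposure and post-exposure prophylaxis, so how long that proportion holds after one dose matters as much as how quickly it is reached. Cohort 4 has the samples to show this up to Day 90, yet its proportion ends at 8 hours. After that the reader gets averages and quantiles. These answer a different question, and the BLQ rule may remove from them the subjects whose NAC has fallen furthest.

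At stake are three descriptive results that the assayed samples could supply: the course of the rate for lot #C2300157 after 8 hours, a single-dose rate at 24 hours and Day 30, and a Day 90 rate with no second dose.

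**Working it through.** The documents give no power, sample-size or expected-rate figure for this endpoint, so there is no planned number to reproduce. The check is a count, followed by two illustrations.

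**1. Cohort 4 times assayed against times with a rate**

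| Post-dose time | Assayed (SAP 3.4) | Rate by endpoint definition | Rate by SAP method text |
|---|---|---|---|
| 2 h | yes | yes | no (9.10.7 gives 4 and 8 h) |
| 4 h | yes | yes | yes |
| 8 h | yes | yes | yes |
| 24 h | yes | no | no |
| Day 30 | yes | no | no |
| Day 45 | yes | no | no |
| Day 90 | yes | no | no |

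The rate covers 3 of 7 times by definition and 2 of 7 by the method text. Four times have none.

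**2. Single-100-mg rates elsewhere**

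Cohort 2 supplies one, at Day 45 before the second dose, for Lots 1 and 2. Its Day 90 and Day 120 rates follow two doses. It is assayed at 24 hours in the first 25 subjects per lot, with no rate planned, and is not assayed at Day 30.

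**3. Can location statistics replace the rate?**

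Assume NAC is log-normal. Let r be the geometric mean divided by the target, with sigma = sqrt(ln(1 + GCV²)). The share below target is Phi(-ln(r)/sigma). The documents give neither r nor GCV, so both are varied.

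| r | GCV 50% (sigma 0.472) | GCV 70% (sigma 0.632) | GCV 100% (sigma 0.833) |
|---|---|---|---|
| 1.5 | 19.5% | 26.0% | 31.3% |
| 2 | 7.1% | 13.6% | 20.3% |
| 5 | 0.03% | 0.5% | 2.7% |

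A geometric mean above target can go with anything from almost nobody to nearly a third of subjects below it.

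**4. Effect of the BLQ rule (hypothetical counts)**

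Suppose 30 subjects are tested at Day 90, six are BLQ after earlier measurable values, 24 are above target, and the lower limit of quantitation (LLOQ) is at or below target.

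- Under SAP 8.3 the six become missing, so n = 30 - 6 = 24. The minimum and every quantile then lie above target. If BLQ also counts as not evaluable in the 9.10.4 denominator, the rate is 24/24 = 100% (exact 95% CI 85.8% to 100%).
- With the six counted as not above target, the rate is 24/30 = 80% (61.4% to 92.3%).

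**5. Precision of the added rows**

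Exact (Clopper-Pearson) 95% intervals at n = 30:

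- 15/30: 31.3% to 68.7%
- 27/30: 73.5% to 97.9%
- 30/30: 88.4% to 100%

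For comparison, an assumed Cohort 2 Day 45 rate near 90% gives 78.2% to 96.7% at 45/50 per lot (if the 2:1 split between PD and PK specimens applies) and 81.7% to 96.2% at 68/75 (if all are tested).

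**The case against.** The SAP follows the Protocol. Protocol 4.2 names 4 and 8 hours as primary times and 2 hours as secondary, and assigns the other PD times to descriptive statistics, which 9.10.9 provides. There is no hypothesis testing, so extra rows are a preference. Subject-level NAC listings let anyone count the share among about 30 people, and the minimum or first quartile shows whether most subjects are above target. The log-normal figures depend on assumed ratios; at r = 5 the problem almost disappears.

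Much of this stands. The endpoint times are not an error, the listings do hold the information, and the log-normal table is only a range. The argument from the minimum and first quartile does not stand as the SAP is written: with later BLQ values set to missing, both can sit above target while some tested subjects are not.

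A reader might infer that the trial never reports how many subjects stay above target after one 100 mg dose. The documents do not support that, because Cohort 2's Day 45 pre-dose rate is such a share and is a primary endpoint. A reader might also take Cohort 4 at Day 90 as the only view of what the second dose adds. That goes too far as well: Cohort 2 has rates before and after its second dose, and its PD parameters are derived by dose where applicable. A Cohort 4 comparison would be non-randomised and across lots, and Cohorts 1-3 had already finished when Cohort 4 was added.

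**Conclusion.** The point holds in this limited form. By endpoint definition, four of the seven Cohort 4 post-dose times have no protective-NAC rate, and on the 9.10.7 wording the 2-hour rate is lost too. The missing results are any rate for lot #C2300157 after 8 hours, any rate after one 100 mg dose at 24 hours or Day 30 in any cohort, and any Day 90 rate without a second dose. The continuous summaries are not a dependable substitute.

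The size of any upward bias is unknown. It depends on how many late samples are BLQ, on the LLOQ (not given), and on SAP 8.3 applying to visit-level NAC summaries as well as to parameter derivation, which its wording allows. If no late sample is BLQ, that bias vanishes and only the missing rows remain. No primary endpoint is invalidated. This is a worthwhile, inexpensive improvement to a descriptive analysis.

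**What to change.** - In SAP 9.10.9, add the frequency-and-percentage rows of 9.10.4, by serotype, at 24 hours and Days 30, 45 and 90 for the assayed Cohort 4 active subjects. Give exact 95% intervals and label the rows descriptive. Do not carry over the 9.10.4 sentence on separate lots, which describes Cohorts 1-2.
- State that a BLQ result from a tested sample counts as not above target and stays in the denominator, provided the LLOQ is at or below that serotype's target. State the LLOQ for each serotype.
- Correct 9.10.7 so that objective and method text both refer to 2 hours.
- Label any comparison with Cohort 2 as non-randomised and across different lots.
- Optionally, add the same rows at 24 hours and Days 8, 15 and 49 for the fully assayed subset of Cohorts 1-2 (25 per dose and lot).

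The cost is SAP wording and a few table rows, with no new samples, assays or subjects and no change to named endpoints. The drawback is more estimates from about 30 subjects, with intervals as wide as those shown above.
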